- fK-I (ALG) (Metal stock tray and irreversible hydrocolloid impression material ("simplified tech.") (7)
- fK-II (ZOE) (Individual tray, border-moulding and zinc-oxide ojenol impression material)
- fK-III (E) (Individual tray, border-moulding and elastomeric impression material)

Direct Digitalization (dD) =

- dD-I (AI-OFF) (Direct impression with intraoral scanner and A.I off)
- dD-II (AI-ON) (Direct impression with intraoral scanner and A.I on)
- dD-III (MOD) (Intraoral scanner and scanning with OR (17) and A.I off)

All measurements will be completed in two sessions and will be performed by a single operator. The first session will last 40 minutes and the fK-I (ALG), dD-I (AI-OFF) and dD-II (AI-ON) group impressions will be completed. First, the lip and cheek will be excluded with an intraoral retractor (OptiView™ Standard Kit) and the dD-I (AI-OFF) impression will be completed by direct scanning with the intraoral scanner (TRIOS4; 3Shape A/S, Copenhagen, Denmark) with the A.I closed. Then, with the same intraoral scanner, the A.I. will be turned on and the impression will be taken again and the dD-II (AI-ON) impression will be completed. Direct scan data will be exported in "STL" format. For fK-I (ALG), the most suitable metal stock tray will be selected and irreversible impression material (TROPICALGIN; Zhermack SpA Badia Polesine (RO), Italy) will be used. Within 10 minutes of impression taking, the impression will be scanned with the same intraoral scanner. A negative of the scan data will be obtained and exported in "STL" format. The individual tray will be designed using a design program (Exocad DentalCAD 2.4 Plovdiv; Emerald Dental Works, Hamilton) and produced with a 3D printer (Photon Mono; Anycubic Tsim SHA TSUI, Kowloon)

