Secondary data will be determined by an evaluation scale asked to the patient to assess patient comfort, taste, nausea, burning sensation after the completion of each measurement. By analyzing the questionnaires and evaluation scales, the opinions of the patients about different measurement methods will be compared.

Statistical Evaluation

In the study, SPSS 20 package program will be used for data analysis. In the analysis of the study, first of all, Kolmogorov Smirnov adaptation test and Shapiro-Wilk test will be used to check whether the data have normal distribution. Afterwards, parametric or non-parametric statistical methods will be used to evaluate whether there is a difference (it is foreseen that independent and dependent group tests, chi-square test, Anova test, and graphs will be given if appropriate). When evaluating the results of the tests, the significance level will be taken as $\alpha=0.05$ and the results will be interpreted according to this critical value.

“Tam Dişsiz Üst Çenede Farklı Ölçü Yöntemlerinin In-Vivo Olarak Karşılaştırılması”

-VAS SKALASI-

Aşağıdaki parametreleri alınan ölçü sırasındaki değerlendirmenize göre 1 ile 10 arasında puanlayınız.

- Ölçü sırasındaki **konfor seviyenizi** değerlendiriniz.

- Ölçü materyalinin oluşturduğu **tat hissini** değerlendiriniz.

- Ölçü materyalinin oluşturduğu **bulantı hissini** değerlendiriniz.

- Ölçü alımı sırasında ağızdaki **yanma hissini** değerlendiriniz.

- Bundan sonraki dental ölçü işlemleriniz sırasında hangi ölçü tipini tercih edersiniz?

Geleneksel ölçü yöntemi

Dijital ölçü yöntemi

REFERENCES

2. Čelebić A, Knezović-Zlatarić D, Papić M, Carek V, Baučić I, Stipetić J. Factors Related to Patient Satisfaction With Complete Denture Therapy. *The Journals of Gerontology: Series A*. 2003;58(10):M948-M53.
3. Cooper LF. The current and future treatment of edentulism. *Journal of Prosthodontics: Implant, Esthetic and Reconstructive Dentistry*. 2009;18(2):116-22.

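### The VAS nausea item asks about nausea created by the impression material, so it may not measure the same thing after a scan as after a conventional impression

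*Combined protocol and SAP*

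**What the plan says.** Under Data Collection, the Secondary Data paragraph provides for "an evaluation scale asked to the patient to assess patient comfort, taste, nausea, burning sensation after the completion of each measurement" and states that "the opinions of the patients about different measurement methods will be compared". The outcome there is nausea, without qualification.

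The VAS form appended to the protocol has a header and four scored items:

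- Header: "Aşağıdaki parametreleri alınan ölçü sırasındaki değerlendirmenize göre 1 ile 10 arasında puanlayınız" (score the following from 1 to 10 according to your assessment during the impression taken).
- Comfort: "Ölçü sırasındaki konfor seviyenizi değerlendiriniz" (rate your comfort during the impression).
- Taste: "Ölçü materyalinin oluşturduğu tat hissini değerlendiriniz" (rate the taste created by the impression material).
- Nausea: "Ölçü materyalinin oluşturduğu bulantı hissini değerlendiriniz" (rate the nausea created by the impression material).
- Burning: "Ölçü alımı sırasında ağızdaki yanma hissini değerlendiriniz" (rate the burning in the mouth during impression taking).

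A last question asks which type of impression, conventional or digital, the patient would prefer in future.

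Materials and Methods defines three conventional methods (fK-I, fK-II, fK-III) and three intraoral-scan methods (dD-I, dD-II, dD-III). The available text gives no separate form for scans, no not-applicable option and no analysis rule for items that name a material.

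**The concern.** Comfort and burning are tied to the procedure. Nausea and taste are tied to a material. For a scan, the nausea item names a cause that was not in the mouth, yet it still asks for a score from 1 to 10.

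Nausea during a scan can have other sources. The documents themselves put devices in the mouth: for the first scan, "First, the lip and cheek will be excluded with an intraoral retractor", and dD-III adds a base and wax template held by adhesive. Whether nausea from these is scored depends on how each patient reads the item.

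At stake is the interpretation of a planned comparison. A lower, equal or higher nausea score for scanning could come partly from the wording. The form does not record what each patient was rating, so no later analysis can separate the two.

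**Working it through.** The plan gives no figure on this point to reproduce. The check sets the item wording beside each procedure and then counts the comparisons concerned.

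**Step 1. Is there an impression material for the item to refer to?** (Materials and Methods)

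| Method | Impression material named | Also placed in the mouth, as described |
|---|---|---|
| fK-I (ALG) | Irreversible hydrocolloid | Metal stock tray |
| fK-II (ZOE) | Zinc-oxide eugenol | Individual tray, impression compound at the border |
| fK-III (E) | Elastomer | Individual tray, impression compound at the border |
| dD-I (AI-OFF) | None | Scanner, retractor |
| dD-II (AI-ON) | None | Scanner (the text does not say whether the retractor stays in) |
| dD-III (MOD) | None | Scanner, base, wax template, adhesive |

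A material is present in 3 of 6 methods and absent, or not named, in the other 3.

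**Step 2. Count the pairs.**

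- All pairs of six methods: 6 × 5 / 2 = 15.
- Conventional versus scan: 3 × 3 = 9. The item has something to refer to on one side only.
- Conventional versus conventional: 3 × 2 / 2 = 3. It has something to refer to on both sides.
- Scan versus scan: 3 × 2 / 2 = 3. It has nothing named to refer to on either side.
- Check: 9 + 3 + 3 = 15.

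**Step 3. Count the scores.** With the minimum of 15 patients given under Sample Size and Power Analysis, there are 15 × 6 = 90 nausea scores, of which 15 × 3 = 45 follow a scan. These 45 are the scores open to the ambiguity. They are not 45 wrong scores.

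**Step 4. Can the direction be settled?** Treat nausea as roughly additive, purely to reason about sign. Let M be nausea from the material, T from the tray and S from the scanner and what goes with it. The whole-procedure contrast, conventional minus scan, is M + T − S. Suppose every patient answers literally and scores nothing for a scan:

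- If patients do not separate tray from material, the recorded contrast is M + T. The error is (M + T) − (M + T − S) = S, which favours scanning.
- If patients do separate them, the recorded contrast is M. The error is M − (M + T − S) = S − T, which may have either sign.
- If patients follow the header and rate the whole procedure, the error is 0.
- If some leave the item blank, the contrast rests on a selected subset and its error is not defined by these terms.

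The documents give no value for M, T or S and no information on how patients will answer. Neither sign nor size follows.

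**The case against.** The best defence is the header. It governs every item and speaks of the impression just taken, and the scale is given straight after each one. A patient who has just been scanned may well rate that scan as a whole. This stands, and it limits the point to ambiguity. A reader might infer that the item certainly measures different things across the methods; the documents do not show that. The header does not remove the problem, though, because the item itself still names the material and patients may resolve the conflict differently.

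A second defence is that a material-only item could be deliberate, since having no material to provoke nausea is a real feature of scanning. This stands in part, and more for taste, which naturally belongs to a material. For nausea it is weaker: devices in the mouth can also cause it, and the Secondary Data paragraph names nausea without tying it to a material.

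A third is that tolerance is measured elsewhere. This stands too: comfort, burning and the preference question do not name a material and remain usable.

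A reader might also extend the point to the two pairs that set alginate in a stock tray against an individual-tray method, on the ground that tray nausea goes unscored. That assumes patients separate the tray from the material it carries, which nothing in the documents supports. The same reasoning would also have to count the pairs of dD-III with dD-I and dD-II, because of the base and adhesive. The count is best left at the 9 conventional-versus-scan pairs.

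**Conclusion.** The point holds as a minor one. The nausea item is narrower than the outcome the protocol names, and it refers to something that two scan methods do not use and the third does not name. It may therefore not measure the same thing in 9 of the 15 pairwise comparisons.

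The conclusion rests on two assumptions: that the form shown is used unchanged after all six methods, and that at least some patients answer the item as worded.

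A reader might infer that the wording biases the trial towards scanning. That follows only if patients answer literally and also count tray nausea as material nausea; under other readings the error can be zero or of either sign. Nor do the documents support a wider reading. Taste is affected less clearly. Comfort, burning, the preference question and the comparison of STL files are not affected.

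**What to change.** **Before data collection:** reword the nausea item on the pattern of the burning item, for all six methods, for example *Ölçü alımı sırasında hissettiğiniz bulantıyı değerlendiriniz* (rate the nausea you felt during impression taking). Rewording taste is optional.

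**If collection has already begun** (the documents do not say): keep the wording, since a change partway would add an inconsistency of its own. Report the item as nausea attributed to the impression material, state the limitation, and do not interpret conventional-versus-scan differences as overall procedural nausea.

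**Cost:** one line on the form (two if taste is included), a form revision and notification of the ethics committee. No extra visits are needed. The reworded item no longer isolates nausea caused by the material alone.
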